13.2 Serious Adverse Events (SAEs)

A SAE is any adverse drug experience that at any dose results in any of the following outcomes :

- Death
- A life-threatening experience
- Subject hospitalization or prolongation of existing hospitalization
- A persistent or significant disability/incapacity
- Congenital anomaly/birth defect

Important medical events that may not result in death, be life-threatening, or require hospitalization may be considered a serious drug experience when, based upon appropriate medical judgment, they jeopardize the health of the subject and may require medical or surgical intervention to prevent one of the outcomes listed in this definition.

In case of unexpected pregnancy for the study subject or study subject's spouse, pregnancy reporting will be completed; for the outcome of the pregnancy and if there are any congenital anomaly.

Non-serious Adverse Event: A non-serious adverse event is any AE, which does not fulfill the definition of a SAE .

Collection, Recording, and Reporting of Adverse Events :

- Any information regarding any adverse event will be collected and reported from the first study related activity till the end of the study and post-treatment follow-up period .
- At each contact, the subject will be asked about adverse events.
- All adverse events, either observed by the Investigator or reported by the subject, will be recorded by Investigator and evaluated .

Adverse events will be assessed at each visit. The subject will be asked about the adverse events. Adverse events will be recorded both in the source document and the CRF. The Investigator needs to record the diagnosis, if available. If no diagnosis will be available, the Investigator records each sign and symptom as an individual adverse event. The patient is given the investigator's number to contact him 24/7 in case of any adverse event.

All adverse events will be collected and recorded by the Investigator on the Adverse Event Form of the CRF and to the monitor for safety reporting. One single Adverse Event Form must be used per adverse event from start to resolution of the event. CIOMS form will be completed for all serious adverse events & reported to the Egyptian Pharmacovigilance Center (EPVC) as per the GVP timelines (During 15 calendar days for SAEs & 90 calendar days for non-serious AEs). Follow-up of all adverse events till resolution or stabilization. The reporting of SAE to the national medicines regulatory authority is a must, within 24 hours of PI notification, as per the IRB/EC of site and RHD of Egyptian MOH.

During subject's participation in the study, the Investigator/Institution will ensure that adequate medical care will be provided to the subject for any adverse event including clinically significant laboratory values related to the study. When the Investigator becomes aware of the adverse event, he/she will inform the subject and does the necessary follow-up.

Only unresolved AEs will be followed up actively until the AE has resolved or stabilized. No active follow-up with the subjects will be made during this period for occurrence of new adverse events.

14 Plans for disseminating & communicating study results

14.1 Progress Report

Timely progress reports will be submitted according to the national medicines regulatory authority. The content of the progress report includes all the available data that are judged relevant to the progress of the study.

14.2 Final Study Report

The final study report will be submitted as soon as possible within 3 months of database lock. If the study is discontinued for any reason; a final report will be submitted and the reasons for terminating will be provided. The title, version and date of the protocol and author will be written in the title page.

The final study report will follow Arab GVP content & include but not limited to:

An abstract of the study, rationale and background, research methods, demographic, baseline characteristics, safety parameters will be analyzed for the total population of all enrolled (randomized) subjects. Efficacy analysis will be performed for the 'Per Protocol populations only. ITT patients will be analyzed for safety in the results section; results and limitations will be discussed in the discussion section of the report.

Population is defined as follows :

- Intention to Treat (ITT): all enrolled subjects with at least one baseline and one post-baseline visit.
- Per Protocol (PP): all enrolled subjects who completed according to the protocol with no protocol deviations.

Continuous variables will be summarized using mean, standard deviation, median, and range (minimum and maximum), while categorical variables will be summarized using proportions (counts and percentages) .

Data on subject disposition (number of subjects enrolled, number of drop-outs, and reasons for drop-out), demographics (gender, age, weight, height), and other baseline characteristics (physical examination results, vital signs, and laboratory assessments) will be summarized.

All biostatistical results and analysis will be done as per endpoints as per protocol, as per section 10.7.

Additionally, for each treatment, the incidences of all treatment emergent AEs will be tabulated by body system and preferred term (to which each AE will be mapped, using World Health Organization Adverse Reaction Terminology (WHO-ART), version 1998/04). Other information regarding AEs, such as intensity, seriousness, causality, and discontinuations due to AEs, will be also tabulated by treatment. AEs that are reported

more than once by a subject will be counted only once for that subject at the maximum intensity.

Concomitant medications will be tabulated by generic drug names, based on World Health Organization Drug Dictionary (WHO-DD), version 1998/04.

15 Confidentiality and publication

Patient names must be kept confidential and should not appear on any CRF page or study specific documents.

The sponsor and health authorities are obligated to respect medical secrecy and to refrain from divulging any personal patient information

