VARIABLES	
Primary Endpoints:
 
1- Primary Safety:
 
 - Incidence of serious/non-serious adverse events 
2- Primary Efficacy:
 
 - Complete resolution for pelvi-abdominal infection based on pelvi-abdominal ultrasound and others and/or clinical response - Complete healing of the of post-operative wounds 
Secondary Endpoints:
 
1- Secondary Safety:
 
 - Presence of any signs/symptoms of post-operative wound infection such as redness, fever or wound discharge. - Change in Total Leukocyte count and Liver enzymes (SGOT, SGPT) between baseline (visit 1) to End of study visit (Follow up 2 V) 
2- Secondary Efficacy:
 
 - Describe complete resolution, improvement, failure or relapse of pelvi-abdominal infection based on pelvi-abdominal ultrasound and others and/or clinical response - Days for complete healing of post-operative wounds after 8 days of treatment (Follow-up 1 V) & 15 days of treatment (End of study visit) between the 2 groups
ASSESSMENT SCHEDULE	
Subjects will be enrolled for 12 months including screening visit
 
 ➤ Visit 1: Screening and treatment initiation visit, Day 0 ➤ Follow-up 1 visit: Day 8 (+/-) 3 days ➤ Follow-up 2 visit & End of study visit: Day 15 (+/-) 3 days
DATA SOURCES	All visits' assessments will be kept in the source files for each patient and in Case Report Form (CRF), which will be verified by the responsible Clinical Research Associate (CRA).
STUDY SIZE	312 patients with pelvi-abdominal infection and/or who started IV antibiotics in post-operative period, for pelvi-

	
abdominal surgeries. They will be randomized by computer, into 2 treatment groups; Ciprofloxacin[®] tablets (Ciprofloxacin/Metronidazole) versus currently used Ciprofloxacin Tablets & Metronidazole tablets, from the surgical department in Menoufia University Hospital and some patients might be referred from other departments in Menoufia University Hospital such as and not limited to; the department of Gynecology and Obstetrics

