10.7 Data Analysis

10.7.1 Analysis populations

Analysis of all efficacy variables will be performed only for patients who completed the study without protocol violation (as per protocol).

Analysis of all safety variables will be performed for all patients (intent-to-treat population), who received even 1 dose of the treatment; either Ciprodiazole[®] tablets or currently used Ciprofloxacin Tablets & Metronidazole tablets.

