10.7.3 Analysis variables

Descriptive Analysis:

- Descriptive analysis of the collected data. All enrolled patients will be included in the safety analysis.
- All quantitative primary and secondary end point variables will be described
- Data from primary and secondary endpoints will be summarized using appropriate summary statistics i.e. n (number of subjects), mean, Standard Deviation (SD), median and range.

Comparative Analysis:

- All tests will be performed on the 5% level of significance.
- Chi² test for unpaired categorical variables.
- Paired t-test to estimate the change in numerical variables throughout the study visits.
- Student t-test to estimate the comparison between the subgroups for the numerical variables.
- *P*-values less than 0.05 will be considered statistically significant

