12.2 Patient Enrollment

After signing the informed consent form, each potential subject will be screened for eligibility based on the inclusion and exclusion criteria specified. Randomization will be done.

All visits will occur as closely as possible to the scheduled visit dates with window of 3 days. In case of a premature discontinuation of the study, the subject, will be, if possible called in for a last visit. Even if the subject would not be able to attend, the 'End of Study' forms will be completed .

12.3 12.3 Schedule of visits

Table 1: Schedule of Visits

Observation	Visit 1 (Screening & treatment)	(Follow-up 1 V)	(Follow-up 2 V) End of Study
Time lines	Day 0	Day 8	Day 15
Informed consent document signed	X		
Review Inclusion/Exclusion criteria	X		
Patient Demographics	X		
Significant medical history and current disease status	X		
Physical examination	X	X	X
Vital Signs	X	X	X
Child-Pugh Score	X		
Concomitant medications	X	X	X
Safety Laboratory Tests:			
FBS	X		
Total Leucocytic count	X		X
SGOT (ALT)	X		X
SGPT (AST)	X		X
Total Bilirubin	X		X
S. Creatinine	X		X
Serum β -HCG: (for females in childbearing period)	X		
Pelvi-abdominal Ultrasound & others (Optional)	X		X
Study Drug Dispensed	X	X	
Drug Accountability		X	X

Observation	Visit 1 (Screening & treatment)	(Follow-up 1 V)	(Follow-up 2 V) End of Study
Time lines	Day 0	Day 8	Day 15
Presence of any signs/symptoms of post-operative wound infection such as redness, fever or wound discharge. (in case of post-operative subjects)	X	X	X
Days for complete healing		X	X
Complete resolution, improvement, failure or relapse of pelvi - abdominal infection		X	X
AE		X	X
SAE		X	X
Study Completion Form			X

The subsequent visits will occur as follows :

- **Visit 1 (Screening & treatment initiation Visit):** Day 0
- **Follow-up V1:** Day 8 (+/-) 3 days
- **Follow-up V2 & End of Study Visit:** Day 15 (+/-) 3 days

12.3.1 Visit 1 (Screening & treatment initiation):

- During this visit, subjects will be informed about the study. If they are willing to participate in the study, they will sign the written ICF. A copy of the signed ICF will be given to the subject. In addition, the subjects will be evaluated for study eligibility according to the inclusion and exclusion criteria.
- Screening Assessments will include: physical examination, vital signs, demographic data (Age & Gender), medical history and concomitant medications.

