8.1 Analysis populations

Analysis of all efficacy variables will be performed only for patients who completed the study without protocol violation (as per protocol).

Analysis of all safety variables will be performed for all patients (intent-to-treat population), who received even 1 dose of the treatment; either Ciprofloxacin[®] tablets or currently used Ciprofloxacin[®] Tablets & Metronidazole[®] tablets.

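### The safety population is defined inconsistently, and the ITT bullet in protocol 14.2, if followed, would drop dosed patients never seen again after visit 1

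*Protocol*

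**What the plan says.** Three rules appear for the safety analysis.

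- **At least one dose.** Protocol 10.7.1: "Analysis of all safety variables will be performed for all patients (intent-to-treat population), who received even 1 dose of the treatment". SAP 8.1 repeats this and uses the same label, "intent-to-treat population".
- **All enrolled.** Protocol 10.7.3: "All enrolled patients will be included in the safety analysis". The synopsis and SAP 8.3.1 carry the same sentence. Protocol 14.2 opens in the same sense: "safety parameters will be analyzed for the total population of all enrolled (randomized) subjects".
- **At least one visit after baseline.** The population list in protocol 14.2 reads "Intention to Treat (ITT): all enrolled subjects with at least one baseline and one post-baseline visit". Section 14.2 ties this to safety: "ITT patients will be analyzed for safety in the results section".

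Section 14.2 also refers the analysis back to section 10.7. The SAP has no visit condition, and its safety table shells print N=156 per arm.

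On timing, the synopsis has "Follow-up 1 visit: Day 8 (+/-) 3 days". For patients who stop early, protocol 12.2 says: "In case of a premature discontinuation of the study, the subject, will be, if possible called in for a last visit".

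**The concern.** The incidence of serious and non-serious adverse events is the primary safety endpoint, and the time frame in protocol 10.7.6 starts at visit 1. A population rule that needs a later visit can therefore remove patients because of what happened to them inside that time frame. Death, and an early event after which the patient does not come back, are the clearest cases.

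The label adds to the risk. ITT means one thing in 10.7.1 and SAP 8.1 and another in the population list of 14.2. Someone programming the tables and looking up ITT would find both. The trial is open label, so if the choice is left until the data are in hand, it is made with treatment and outcome visible.

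**Working it through.** The question is mainly one of comparing passages. The arithmetic at the end is an illustration only.

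**1. Which patients separate the rules?**

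| Patient | At least one dose (10.7.1, SAP 8.1) | All enrolled (synopsis, 10.7.3, SAP 8.3.1, 14.2 opening) | 14.2 ITT bullet |
|---|---|---|---|
| Dosed, seen at any later visit | in | in | in |
| Dosed, never seen again after visit 1 | in | in | **out** |
| Randomised, no dose taken, never seen again | out | in | out |
| Randomised, no dose taken, seen later | out | in | in |

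The first two rules differ only for patients who are randomised and take nothing. Protocol 12.3.1 puts randomisation and the first study drug at visit 1, so that group should be very small. The row that matters is the second.

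**2. Can a patient in that row have a recorded event?** Yes.
- The first scheduled visit after baseline is Day 8 ± 3, that is Day 5 to Day 11.
- Protocol 10.2.3 lists SAE or death, and loss to follow-up, as reasons for leaving the study.
- After withdrawal for an adverse event, 10.2.3 allows follow-up by visit or by telephone.
- The last visit in 12.2 is conditional on being possible.
- Protocol 13.2 collects adverse events from the first study activity and gives patients a number to call at any hour.

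So an early SAE or death can be in the database for a patient with no visit after baseline.

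**3. Do other passages settle the conflict?** Not fully. Section 10.7, to which 14.2 refers, holds both the one-dose and the all-enrolled rule. The SAP repeats both and does not mention the visit rule, either to adopt it or to withdraw it. The N in its shells is 312/2 = 156 per arm, which corresponds to all randomised patients.

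**4. Illustration of size.** The documents give no rate of early loss or of SAEs. Assume an arm of 156 with e SAE patients, m patients with no visit after baseline, and k of those m with an SAE. The proportion changes from e/156 to (e − k)/(156 − m). Take e = 4, so 4/156 = 2.6%.

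| m | k | Under the 14.2 bullet |
|---|---|---|
| 3 | 1 | 3/153 = 2.0% |
| 8 | 1 | 3/148 = 2.0% |
| 8 | 2 | 2/148 = 1.4% |
| 8 | 4 | 0/148 = 0% |
| 16 | 1 | 3/140 = 2.1% |
| 16 | 2 | 2/140 = 1.4% |

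The proportion falls whenever k/m exceeds e/156, that is, when SAEs are commoner among the patients not seen again than in the arm as a whole. If none of 8 such patients had an SAE, it would rise slightly, to 4/148 = 2.7%.

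If the second arm also had 4/156 but lost nobody, the row m = 8, k = 2 would turn equal arms into 1.4% against 2.6%, a difference of 1.2 percentage points produced by the rule alone.

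**The case against.** The documents as a whole lean towards keeping these patients. Section 14.2 itself says safety covers all enrolled subjects and sends the analysis to section 10.7, where no visit condition exists. The SAP has none either, and its shells use all randomised patients. The restrictive wording occurs once, in a section about reporting.

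The group at risk is also narrow. The bullet asks for any visit after baseline, not the Day 8 visit. Patients who stop for an adverse event are followed up, and those who discontinue are called in where possible, so many early stoppers would have a qualifying visit.

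All of this stands, and it rules out three stronger readings that a reader might infer:
- That the plan does exclude patients with early SAEs. It contradicts itself; it does not settle on exclusion.
- That anyone who stops early for a reaction is lost. Only those never seen again are: deaths, patients who do not return, and those followed by telephone only.
- That there are three materially different safety sets. In substance there are two near-identical sets and one outlier.

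What the objection does not remove is that 14.2 is the place where the protocol formally lists its populations, and that it directs ITT patients to the safety results. A report that followed that list would be following the protocol.

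**Conclusion.** The inconsistency is real and should be removed before database lock. The one-dose and all-enrolled rules probably select almost the same patients. The 14.2 bullet does not: if it were applied, it would take dosed patients with no further visit out of the primary safety analysis even when an SAE or death is on record.

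This could understate harm. It could do so unequally, because in an open-label trial the decision not to return may depend on the known treatment. The documents do not show that it would, or in which direction.

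The size is unknown. The fall from 2.6% to between 2.1% and 0% in the working rests on assumed counts of 4 SAE patients per arm and 3 to 16 patients without a later visit, with at least one SAE among the latter. It shows only that, with few events, losing one or two changes the result.

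**What to change.** - Define one named safety set: all randomised patients who took at least one dose of study treatment.
- Delete the condition of a visit after baseline from the ITT bullet in protocol 14.2.
- Refer to the one safety set in the synopsis, protocol 10.7.1 and 10.7.3, the opening sentence of 14.2, SAP 8.1 and SAP 8.3.1. Stop using the ITT label for it.
- In the SAP safety tables (Tables 4 to 8 and 11 to 14), replace the fixed N=156 with the actual number in the safety set per arm.

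The cost is wording in these places and in the table shells. No new data, visits or patients are needed. Protocol 10.7.2 and SAP 8.2 already provide for a final SAP before database lock in which such differences are identified and documented.

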15.1 Use of information

The study data are the property of the sponsor (Minapharm Pharmaceuticals). The investigator and any of the research staff shall obtain written approval from the sponsor prior to the publication/communication of the results of any work carried out during or in relation to the study

16 Archiving

The investigators should retain all essential study-related documents e.g. signed protocol, investigator's brochure, CRFs, medical records, laboratory reports, etc. in accordance with the applicable regulatory requirements of his/her country.

The study-related documents should be kept together in the investigator site file provided to the investigator by the sponsor for minimum 5 years.

17 Responsibility of Participants

17.1 Responsibility of Investigators

The investigators will conduct the study in accordance with ICH-E6, all applicable laws in the country where the study is conducted and in accordance with this study protocol

The responsibilities of the investigator are summarized below but not limited to:

1. Patient's information and consent
2. Information on the overall results of the study
3. Information to other practitioners
4. Adverse Events recording
5. Data Recording in paper CRF
6. Record Retention
7. Use of study-related information
8. Medicinal Product
9. Quality Control
10. Study Discontinuation
11. Delegation of investigator duties
12. Study Agreement Discontinuation
13. Collect unused/returned drug from patients

14. Return collected unused/returned drugs to CRO; on behalf of Minapharm

17.2 Responsibility of CRO:

1. Design and write the protocol.
2. Design the statistical section of the protocol
3. Design CRFs
4. Design informed consent
5. Collect regulatory documents (EC of site and RHD of MOH)
6. Develop investigator agreement template
7. Prepare investigator's signatures on participation in study
8. Prepare Ethics Committee/ RHD of MOH file
9. Ethics Committee followed by RHD of MOH submissions and collecting approvals.
10. Follow up reports to Ethics Committee / RHD of MOH
11. Design & distribute study site staff manual
12. Train study site staff for GCP, CRF completion and safety notification: PI, co-investigators & rest of site staff
13. Conduct initiation visits
14. Set up trial master file (TMF) and Investigator Site File (ISF) for Principle Investigators
15. Design study tracking system
16. Randomization list
17. Provide pharmacy briefing (temperature & etc.,)
18. Conduct drug accountability
19. Collect unused/returned drug from investigators
20. Destroy unused/returned drug
21. Conduct SIV, Follow-Up Monitoring visits and Close out visits.
22. Provide site management
23. Resolve CRF queries
24. Provide project management services
25. Revise SAE reports and send all AE cases (serious & non-serious) to EC & regulatory (RHD of MOH and EPVC)
26. Prepare and submit regular interim report to EC of site and RHD of MOH including safety reporting of all adverse events whether serious or non-serious.
27. Design/build database

28. Generate queries
29. Lock database
30. Ship project-related documents to Sponsor
31. Create statistical analysis plan
32. Write statistical report
33. Write interim and final clinical study report
34. Write publication manuscript
35. Assist on publication of paper in medical journal

17.3 Responsibility of the Monitor

The responsibilities of the study monitor are defined in ICH-E6, Chapter 5. The monitor, who is mandated by the sponsor, must ensure that the study is conducted in accordance with GCP guidelines and all applicable local laws and that the rights, the security and well-being of the patients are respected.

Responsibilities include:

1. Communication
2. Training
3. Compliance
4. Source Data Verification
5. IP (in association with the sponsor).

17.4 Responsibility of the Sponsor

The sponsor; the pharmaceutical company (MINAPHARM) which is responsible and initiates the clinical investigation.

Responsibilities include:

1. Selecting qualified investigators.
2. Determine investigator budget.
3. Providing the investigators with the information they need to conduct an investigation properly.
4. Identify the laboratory and other investigation centers
5. Prepare Contract for laboratory
6. Contracting an insurance company for the clinical study
7. Ensuring proper monitoring of the investigation.
8. Ensuring that the investigation is conducted in accordance with the general investigational plan and protocol.
9. Shipping medicinal new drugs only to sites which are participating in the investigation.
10. Giving each participating clinical investigator/ site an investigator brochure.

11. Reviewing and evaluating the evidence related to the safety and effectiveness of the drug as it is obtained from the investigator.
12. If determining that its medicinal drug presents an unreasonable and significant risk to subjects, the sponsor will discontinue those investigations that present the risk, notify the medicine authorities, all institutional review boards and all investigators who have at any time participated in the investigation of the discontinuance.
13. Reporting all adverse events to EPVC (Egyptian Pharmacovigilance Center) as per the GVP timelines

